The total duration of study participation will be up to approximately 13 weeks. Patients will be screened for participation within 3 weeks of dosing (Days -21 to -1). The Treatment Period will consist of injections of SAN-300 or placebo over a period of 6 weeks, concluding with the End-of-Treatment Visit (Days 1 to 43). The Follow-up Period will consist of an additional 4 weeks (Days 43 to 71).

Safety Assessments:

Safety assessments will consist of the following: physical examinations, vital sign measurements, 12-lead electrocardiograms (ECGs), laboratory parameters, AEs, and concomitant therapy use.

Pharmacokinetic Assessments:

Pharmacokinetic parameters for SAN-300 will be estimated using a population based approach with nonlinear mixed-effect modeling, in accordance with the FDA Draft Guidance on Population Pharmacokinetics (1999). In addition, exploratory assessments of linearity across doses/regimens, accumulation after repeated dosing and pharmacokinetic/pharmacodynamic relationships will be performed.

Pharmacodynamic Assessments:

PD parameters will consist of VLA-1 receptor occupancy (VLA-1 saturation assay); an immunophenotyping panel (CD3, CD4, CD8, CD14, CD19, CD45, CD45RO, and CD49 α); CRP; and cytokines (interferon-gamma [IFN γ], tumor necrosis factor-alpha [TNF α], interleukin-6 [IL-6]).

Efficacy Assessments:

Efficacy evaluations will consist of changes from baseline in the Disease Activity Score with 28-joint count using CRP (DAS28-CRP), ACR Core Set Measurements, the Health Assessment Questionnaire – Disability Index (HAQ-DI), and magnetic resonance imaging (MRI) of the hand and wrist most clinically affected by RA. Each MRI will be scored using the Outcome Measures in Rheumatology Clinical Trials (OMERACT) RA MRI scoring (RAMRIS) system.

Primary Efficacy Endpoint:

DAS28-CRP mean change from baseline to the End-of-Treatment Visit

Secondary Efficacy Endpoints:

- American College of Rheumatology 20 (ACR20) responder rate at the End-of-Treatment Visit
- DAS28-CRP ≤ 3.2 and < 2.6 responder rates at the End-of-Treatment Visit
- ACR50 and ACR70 responder rates at the End-of-Treatment Visit
- Change in HAQ-DI at the End-of-Treatment Visit
- MRI findings of the hand and wrist most clinically affected by RA at the End-of-Treatment Visit

Other Laboratory Assessments:

Other laboratory parameters include anti-SAN-300 antibody levels, rheumatoid factor (RF), antinuclear antibody (ANA), and anti-citrunillated peptide antibodies (ACPA).

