7.2 Procedures for Early Withdrawal

When it is determined that a patient should withdraw from the study, the reason(s) must be recorded, final assessments must be scheduled, and provisions for the continued treatment of RA within the standards of care must be discussed with the patient. Safety and study endpoint evaluations for the Early Withdrawal Visit (see Sections 10.2.6 and 10.3.1) will be performed as soon as possible after the decision is made to withdraw the patient.

Additional interventions (concomitant medications or therapies) may be prescribed as needed by the patient. The patient's history and preferences should be considered and discussed when prescribing a new medication for RA.

Appropriate medical follow-up with the patient should be conducted as clinically indicated after the Early Withdrawal Visit. Telephone contacts between the patient and the study staff should be conducted as frequently as needed.

If the patient is found to have an AE or clinically significant laboratory abnormality, the patient will be followed until the event/abnormality is resolved, or until the Investigator determines that further follow-up is no longer medically indicated. The responsible IEC/IRB should be notified of any AEs and/or circumstances leading to early withdrawal.

Amendment 5: 28 Mar 2016

If a patient is withdrawn from study participation because of pregnancy, Product Safety and IEC/IRB should be informed by the site within 24 hours of awareness. All pregnancies occurring in female patients must be reported. The pregnancy will be reported according to the procedures provided in Section 9.8. Should the patient have a spontaneous abortion or complications during the pregnancy, then the event must be captured as an SAE. Sites are obligated to follow the patient until the outcome of the pregnancy is known. The patient and/or her treating physician should be encouraged to report any future medical problems the child develops of which they become aware that are considered related to the study drug.

Patients who are randomized and who subsequently withdraw from the study will not be replaced.

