Notes: Patients will be randomized to each cohort in a 3:1 ratio of SAN-300 to placebo. A Safety Committee Review will occur after patients have completed the 6-week Treatment Period of

each cohort. Any subject who withdraws prior to the end of the 6-week Treatment Period will not be replaced and the Study Safety Committee will review the data from all subjects regardless of duration of participation in the study.

Figure 2 provides a study schematic indicating visit structure for each individual cohort. After initial Screening, eligible patients will return to the study site at weekly intervals throughout the Treatment Period for study drug administration and safety, PK, PD, efficacy, and other assessments. Enrolled patients will also return to the study site between study drug administration visits for the assessment of PK/PD endpoints. Primary and secondary efficacy endpoints will be assessed at the End-of-Treatment Visit on Day 43. During the 4-week Follow-up Period, patients will return to the study site at 2 weeks and 4 weeks after the end of the Treatment Period for additional assessments.

Primary Efficacy Endpoint Randomization Last Visit Screening Treatment Period Follow-up Period SAN-300 SC (N=30) Screening Period Placebo SC (N=10) Visit: 1 3 4 5 6 9 10 2 7 8 Day: -21 1 8 15 22 29 36 43 57 71 Week: 1 7 11 Last weekly SAN-300 dose Last every-other-week SAN-300 dose

Figure 2. Study Design for Individual Cohorts

Abbreviation: SC = subcutaneously.

Screening: Between Days -21 and -1. Informed consent will be obtained before any study specific procedures are performed. Eligibility assessments will be performed.

Treatment Period: Days 1 to 43. Baseline assessments and measurements will be performed before dosing with study drug. Patients will receive SC injections of study drug as follows:

• For all cohorts, patients randomized to receive placebo will be administered a total of six once-weekly injections of placebo on Days 1, 8, 15, 22, 29, and 36.

- In Cohorts A, B, E and F, patients randomized to receive SAN-300 will be administered a total of six weekly injections of SAN-300 on Days 1, 8, 15, 22, 29, and 36.
- In Cohorts C and D, patients randomized to receive SAN-300 will be administered a total of three every-other-week injections of SAN-300 on Days 1, 15, and 29 and will be administered a total of three every-other-week injections of placebo on Days 8, 22, and 36.

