Study assessments and measurements will be performed on Days 1, 8, 15, 22, 29, 36, and 43. Patients will also visit the clinic between study drug administration visits for the assessment of PK/PD endpoints. The primary and secondary efficacy endpoints will be assessed at the End-of-Treatment Visit on Day 43.

Study procedures at each visit are described in the Schedule of Assessments, provided as Appendix 1.

Follow-up Period: Days 43 to 71. Study patients will return for follow-up visits on Days 57 and 71 for safety and efficacy assessments. The Exit Visit will occur on Day 71. Patients who withdraw early from the study must return to the clinic to complete the Exit Visit assessments.

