4 GENERAL CONSIDERATIONS FOR DATA ANALYSIS

All statistical testing will be two-sided with an alpha level of 0.05. Any p-values displayed will be rounded to four decimal places, with p-values below 0.0001 displayed as '<.0001', and p-values above 0.9999 displayed as '>.9999'.

Categorical variables will be summarized by frequency counts and percentages for subjects in each category. Percentages will contain one decimal place. In cases of zero frequency counts, the percentage will not be reported.

Continuous variables will be summarized with the number of observations (n), mean, standard deviation (SD), median, minimum, and maximum. The mean and median will be presented to one decimal place more than the captured data. The SD will be presented to two decimal places

more than the captured data. The minimum and maximum will be presented to the same precision as the captured data.

Study day will be calculated as follows:

- Assessments/events prior to the first dose date, study day will be the assessment date minus the first dose date.
- Assessments/events on or after the first dose date, study day will be the assessment date minus the first dose date plus one.

Baseline is defined to be the last non-missing assessment (including assessments measured at unscheduled visits) before receiving the first dose of the study medication.

End of treatment (EOT) value is defined as last available post-baseline value during the treatment period.

Subjects will be identified in listings by center number and subject number. Unless otherwise specified, all listings will be sorted by randomized treatment, subject identification number and visit (if applicable).

Efficacy analysis will be performed on the Intent-to-Treat (ITT) population by treatment group to which subjects were randomized. Safety analysis will be performed on the Safety population by treatment received.

Parameters presented by "treatment group" will display the patients on SAN-300 from each cohort and the pooled patients on placebo, unless otherwise indicated.

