9 STATISTICAL AND ANALYTICAL ISSUES

9.1 Handling of dropouts or missing data

Subjects who prematurely discontinue before the end of the treatment will be contacted via follow-up phone call as frequently as needed. If the patient is found to have an AE or clinically significant laboratory abnormality, the patient will be followed until the event/abnormality is resolved, or until the Investigator determines that further follow-up is no longer medically indicated.

For subjects who discontinue prematurely, the last completed post-baseline assessment will be used as EOT.

Missing data will not be imputed in other analyses unless specified otherwise.

For subjects who terminate early from the study, if the study day of the EOT visit falls into a specific protocol defined scheduled visit window, the EOT visit will be reassigned to that specific scheduled visit for the analyses by protocol defined scheduled visit.

For cases where the start date of an AE is not complete, the assumption is made that the AE is a treatment-emergent event unless there is evidence to the contrary.

For cases where the start or the stop date of medication is not complete, the assumption is made that the medication is a concomitant medication unless there is evidence to the contrary.

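### SAP 9.1 omits the treatment-period limit that SAP 4 puts on the end-of-treatment value, neither section excludes values after new RA therapy, and early withdrawals can count as responders

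*SAP*

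**What the plan says.** SAP 4 gives the general rule: "End of treatment (EOT) value is defined as last available post-baseline value during the treatment period". SAP 9.1 gives a rule for premature discontinuers: "the last completed post-baseline assessment will be used as EOT". Section 9.1 does not refer back to SAP 4 and sets no time limit.

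SAP 3.1 defines the period by calendar ("Treatment Period: Days 1 to 43") and fixes the time point: "The primary and secondary efficacy endpoints will be assessed at the End-of-Treatment Visit on Day 43". The first secondary efficacy endpoint in the protocol synopsis is worded to match: "American College of Rheumatology 20 (ACR20) responder rate at the End-of-Treatment Visit". Beyond the last-value rule, SAP 9.1 states: "Missing data will not be imputed in other analyses unless specified otherwise". Neither document has a non-responder rule. For early terminators whose last visit falls in a scheduled window, SAP 9.1 adds that "the EOT visit will be reassigned to that specific scheduled visit for the analyses by protocol defined scheduled visit".

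On visits, Protocol 3.1 and SAP 3.1 require early withdrawals to come back for the Exit Visit assessments. DAS28-CRP and the ACR core set are measured at the Treatment Period withdrawal visit (Protocol 10.2.7). They are measured again on Days 57 and 71 and at a follow-up withdrawal visit (Protocol 10.3.2). On leaving the study, Protocol 7.2 states: "Additional interventions (concomitant medications or therapies) may be prescribed as needed by the patient". It asks for the withdrawal visit promptly but does not place it before or after the start of new therapy.

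**The concern.** The end-of-treatment value feeds the primary efficacy comparison (DAS28-CRP change) and the ACR and DAS28-CRP responder comparisons. If one section bounds that value by the treatment period and another does not, two programmers can derive different values for the same patient. If nothing excludes values taken after new RA therapy, the value can reflect a drug other than the one randomized. And if a patient who left before Day 43 can count as a responder, the reported rate is not quite a rate of response at the Day 43 visit. SAP 3.5 says the results will be used to design later efficacy studies, so the rates matter even though this study is not powered.

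**Working it through.** Neither document has a figure that depends on this rule, so there is nothing to reproduce. The check is a comparison of text, followed by simple arithmetic on size.

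**Step 1. Where the two sections diverge.** They differ only if a discontinuing patient has an efficacy value after the Treatment Period. The cases below are hypothetical and use nominal visit days.

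| Patient | SAP 4 value | SAP 9.1, read literally |
|---|---|---|
| Last dose Day 15, withdrawal visit Day 22, nothing later | Day 22 | Day 22 |
| Same patient, Exit Visit assessments done on Day 71 | Day 22 | Day 71, which is 71 − 15 = 56 days after the last dose |
| Completes Day 43, leaves at Day 57 | Day 43 | Day 57 |

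In the third row, Day 57 is 57 − 36 = 21 days after the last weekly dose, or 57 − 29 = 28 days after the last active every-other-week dose. The sentence in SAP 9.1 that opens the topic concerns patients who stop before the end of treatment, so this row was probably not intended. The operative sentence nevertheless says only that the patient discontinued prematurely.

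**Step 2. Values after new RA therapy.** Protocol 7.1 lists as withdrawal reasons both RA worsening that needs immediate treatment and use of a non-permitted medication. In the second case, if the medication was an anti-arthritic (barred by Protocol 6), the withdrawal visit necessarily follows it. SAP 4 does not close this gap either: the Treatment Period is a calendar span, so a value on Day 30 counts whether or not study drug has stopped and other therapy has begun.

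**Step 3. Responder status.** Under either section, a patient who withdraws on, say, Day 22 and meets ACR20 at that visit is a responder in the end-of-treatment analysis. The per-protocol population (SAP 4.1) is the planned sensitivity analysis. It is defined by one inclusion and two exclusion criteria, so it does not remove withdrawals.

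**Step 4. Size.** Protocol 11.1 compares 6 active patients per cohort with 10 pooled placebo patients.

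- One patient in an active arm: 1/6 = 16.7 percentage points.
- One patient in placebo: 1/10 = 10 percentage points.

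With hypothetical counts of 5/6 versus 2/10, the smallest expected counts are 6 × 7/16 = 2.6, 6 × 9/16 = 3.4 and 10 × 7/16 = 4.4. More than one is below 5, so Protocol 11.1 calls for Fisher's exact test. Two-sided p = 0.035. Recoding one active responder as a non-responder gives 4/6 versus 2/10, p = 0.118.

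The documents give no dropout rate. Over an assumed range of 5% to 20%, the chance of at least one withdrawal in an arm of 6 is 1 − 0.95^6 = 26% to 1 − 0.80^6 = 74%.

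**The case against.** The best reply is that SAP 4 defines the term and SAP 9.1 merely applies it to discontinuers. On that reading the treatment-period limit carries over and there is no conflict. This is plausible, and in most cases the two sections do give the same value. But 9.1 does not say so, and the Exit Visit requirement gives a route to a later value.

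Several stronger conclusions are tempting, and the documents do not support them:

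- *That response rates will be inflated in arms with more withdrawals.* A last-value rule can also lower rates, when patients leave before benefit appears. The direction cannot be known from the plan.
- *That patients leaving for worsening RA will be scored as responders.* Protocol 10.2.7 gives the Treatment Period withdrawal visit the same procedures as Visit 8, including the efficacy measures. The last value would usually show the worsening. An earlier response is carried forward only if that visit or its efficacy data are missing.
- *That early withdrawals enter the Day 43 column.* The window reassignment in SAP 9.1 protects the by-visit tables. Only the end-of-treatment analyses are affected.
- *That new therapy will routinely come before the withdrawal assessment.* Protocol 6 bars other anti-arthritic treatment during the study, and Protocol 7.2 asks for the visit promptly. The documents leave the order open; they do not show that it will occur.

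It is also fair to say that efficacy is a secondary objective, the study is unpowered, individual data are listed, and a last-value endpoint stated in advance is a legitimate choice. These points limit the weight of the concern. They do not supply the missing limit in 9.1 or an analysis that shows how much the result depends on withdrawals.

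**Conclusion.** The point holds in a narrow form. SAP 9.1 lacks the limit in SAP 4 and, read literally, can select a value from after the Treatment Period or replace an observed Day 43 value. Neither section excludes values after new RA therapy. In the end-of-treatment analyses, a patient who withdrew before Day 43 can count as a responder, and no planned analysis shows the effect of that choice.

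The size is 16.7 or 10 percentage points per patient affected. Any patient carries that weight in groups this small, so the figure shows sensitivity and does not estimate bias. The p-values and withdrawal probabilities rest on assumed counts and rates. The group sizes are the protocol's; SAP 3.5 reports 41 randomized without giving the split. The matter is worth correcting because the repair is small, but it does not undermine the study's primary purpose, which is safety.

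**What to change.** Use one definition in SAP 4 and SAP 9.1: the end-of-treatment value is the last post-baseline value within the Treatment Period, through the Day 43 visit window (Day 43 + 2 = Day 45 under the visit allowance in Protocol 10.2), and before the start of any new RA therapy. State that values from later visits are never used as the end-of-treatment value, including for patients who leave during follow-up.

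For the ACR20/50/70 and DAS28-CRP cut-off endpoints, count patients who withdrew before Day 43 as non-responders in the main analysis, and show the last-value result as a sensitivity analysis.

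The cost is a few SAP sentences and one extra table. No new data are needed, because Protocol 6 already requires all medication to be recorded until the patient completes the study. The downside is that reported responder rates may be lower.

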10 INTERIM ANALYSES AND DATA MONITORING

There will be no formal interim analysis during the course of the study.

APPENDIX 1 OVERALL TIME AND EVENTS SCHEDULE

	Screening											Follow-	up Period
STUDY ASSESSMENTS	(21 days)				-	Гreatment Р	eriod					(28	days)
Week:		Wee	k 1	Week 2	Week 3	Week 4	We	ek 5	Wee	ek 6	Week 7	Week 9	Week 11
Visit:	Visit 1	Visi	t 2	Visit 3	Visit 4	Visit 5	Vis	sit 6	Vis	it 7	Visit 8	Visit 9	Visit 10
Day	-21 to -7	Day 1 ^a		Day 8 ^a	Day 15 ^a	Day 22 ^a	Day 29 ^a		Day 36 ^a		Day 43 ^a	Day 57 ^a	Day 71 ^a
Timing (where applicable):		Pre- dose	Post- dose				Pre- dose	Post- dose	Pre- dose	Post- dose	ЕОТ		Exit Visit
Eligibility Assessments												•	
Informed Consent	X												
Inclusions/Exclusions	X	X											
Demographics	X												
Medical History	X	X											
Medication History	X	X											
RA History and Prior RA Treatment	X	X											
HCV Antibody, HBsAg, HIV Antibody	X												
Chest X-ray ^b	X												
QuantiFERON-GOLD	X												
Dosing													
Randomization		X											
Administration of SAN-300 or Placebo ^c		X ^d		X ^c	X	X ^c	X		X ^c				
Safety Assessments													
Vital Sign Measurements	X	X	X ^g	X ^g	X ^g	X ^g	X	X ^g	X	X ^g	X	X	X
Physical Examination	X	X									X		X
CBC, Chemistry Panel	X	X		X	X	X	X		X		X	X	X
UA	X	X									X		X

	Screening											Follow-	up Period
STUDY ASSESSMENTS	(21 days)		Treatment Period							(28 days)			
Week:		Wee	k 1	Week 2	Week 3	Week 4	We	ek 5	Wee	ek 6	Week 7	Week 9	days) Week 11 Visit 10 Day 71 ^a Exit Visit X X X
Visit:	Visit 1	Visit 2 Day 1 ^a		Visit 3 Day 8 ^a	Visit 4	Visit 5	Visit 6 Day 29 ^a		Visit 7 Day 36 ^a		Visit 8	Visit 9	Visit 10
Day	-21 to -7				Day 15 ^a	Day 22 ^a					Day 43 ^a	Day 57 ^a	Day 71 ^a
Timing (where applicable):		Pre- dose	Post- dose				Pre- dose	Post-dose	Pre- dose	Post- dose	ЕОТ		Exit Visit
INR, PT, aPTT, Complement		X											
Serum Immunoglobulins		X									X		X
Pregnancy Test	Serum	Urine				Urine			Urine		Serum		
Adverse Events	X	X	X	X	X	X	X	X	X	X	X	X	X
Concomitant Medications		X	X	X	X	X	X	X	X	X	X	X	X
Efficacy Assessments													ı
ACR Core Set Assessments, DAS28-CRP	X	X		X	X	X	X		X		X	X	X
HAQ-DI	X	X		X	X	X	X		X		X	X	X
ESR	X	X		X	X	X	X		X		X	X	X
CRP	X	X		X	X	X	X		X		X	X	X
MRI of Hand and Wrist ^f		X									X		
Other Assessments								1			I.		
RF, ACPA	X										X		
ANA		X									X		

Abbreviations: ACPA = anti-citrunillated peptide antibodies; ACR = American College of Rheumatology; ANA = antinuclear antibody; aPTT = activated partial thromboplastin time; CBC = complete blood count with differential and platelet count; CCP = cyclic citrullinated peptide; DAS28-CRP = Disease Activity Score with 28-joint count C-reactive protein; ECG = electrocardiogram; ESR = erythrocyte sedimentation rate; HAQ-DI = Health Assessment Questionnaire – Disease Index; HBsAg = hepatitis B surface antigen; HCV = hepatitis C virus; HIV = human immunodeficiency virus; CRP = C reactive protein; INR = international normalized ratio; MRI = magnetic resonance imaging; PT = prothrombin time; QFT = QuantiFERON®-TB Gold test; RA = rheumatoid arthritis; RF = rheumatoid factor; UA = urinalysis.

^a Weekly visits during the Treatment and Follow-up Periods can be scheduled for ±2 days around each of the designated Days in this schedule, but the designated Days themselves will not be shifted relative to Day 1.

b If a chest X-ray was performed with no clinically significant findings within 1 month of randomization, another chest X-ray is not required at Screening.

^c For all cohorts, patients randomized to receive placebo will be administered a total of 6 once-weekly SC injections of placebo on Days 1, 8, 15, 22, 29, and 36.

In Cohorts A, B, and D, patients randomized to receive SAN-300 will be administered a total of 6 once-weekly SC injections of SAN-300 on Days 1, 8, 15, 22, 29, and 36. In Cohorts C and E, patients randomized to receive SAN-300 will be administered a total of three every-other-week SC injections of SAN-300 on Days 1, 15, and 29 and will be administered a total of three every-other-week SC injections of placebo on Days 8, 22, and 36. Note: Subject to be observed at minimum 1 hour post- dose. Longer observation allowed if deemed necessary by investigator or designee.

^d Day 1 dosing will occur on the day of or within 24 hours after randomization.

e After baseline assessment, additional assessments of tryptase and histamine to occur only in suspected cases of anaphylaxis or hypersensitivity reactions.

f In patients who are able to tolerate the MRI, it should be performed within 5 days prior to or at Visit 2 (Day 1, prior to dosing). MRI of hand and wrist most clinically affected by RA will be imaged at Baseline, the same wrist will be imaged at End of Treatment.

^g Blood pressure and pulse will be collected at the end of the observation period; prior to the subject leaving the clinic. When a post-dose blood sample is collected, the blood pressure and pulse should be assessed prior to the sample collection

